SUD period: defined as the period between a patient's first 44mg/1.1mL vial of elranatamab and first 76mg/1.9mL vial of elranatamab, inclusive. See Section 9.3.1 and Annex 1 for more details. Within the SUD period, three sub-periods are identified:

- **Overall:** defined as the period between first 44mg/1.1mL vial and first 76mg/1.9mL vial of elranatamab.
- **First 44mg/1.1mL vial – Second 44mg/1.1mL vial:** defined as the period between the two 44mg/1.1mL vials of elranatamab, if second 44mg/1.1mL vial is administered.
- **Second 44mg/1.1mL vial – first 76mg/1.9mL vial:** defined as the period between the second 44mg/1.1mL vial and the first 76mg/1.9mL vial of elranatamab, if second 44mg/1.1mL vial is administered.

Follow-up period: defined as the period between the first hospital claim for elranatamab (index date) and the end of the hospital claim of the last elranatamab administration. Within this follow-up period, five sub-periods are identified (when sufficient follow-up time is available at the patient level). These sub-periods allow for reporting study endpoints across different phases of the follow-up period, and are based on expected dosing administrations and schedule of patients with switch to bi-weekly administrations from label guidance (see [Table 10. Dosing Schedule of Elranatamab during Follow-up Period for Patients Switching to](#)

[Q2W](#) and [Table 11. Dosing Schedule of Elranatamab during Follow-up Period for Patients staying on QW](#)):

- **Index date to day 8:** defined as the first 8 days post-index date, inclusive. Also defined as day 1 to day 8.
- **Day 9 to day 168:** defined as the period from day 9 to day 168 post-index date.
- **Day 169+:** defined as the period from day 169 post-index date to end of follow-up period.

- **Overall follow-up:** defined as the period from index date to end of follow-up period.

IVIG follow-up assessment period: defined as the 30-day window post index date. If a patient has fewer than 30 days of data available post to the index date, the assessment window will be equal to the maximum number of days available post to the index date.

CRS/ICANS follow-up assessment period: defined as the 14-day window post index date. If a patient has fewer than 14 days of data available post to the index date, the assessment window will be equal to the maximum number of days available post to the index date.

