Table 2 summarizes the patient exposure groups and assessment periods during which endpoints for each study objective will be measured. Patients will be included in the follow-up sub-period analyses if they have at least one claim for elranatamab or if the end date of their follow-up period falls within the sub-period's time frame.

Table 2. Patient Exposure Groups Stratification and Assessment Period for Study Objectives

Study Objective	Assessment period	Patient Exposure Groups
Objective 1 – Patient Characteristics	Baseline period	Study population
	Index date	Group A, Group A+B, Group C
Objective 2 – Treatment administration, dosing and timing	SUD period 
 Overall (Between first 44mg/1.1mL vial – first 76mg/1.9mL vial) Between first 44mg/1.1mL vial – second 44mg/1.1mL vial Between second 44mg/1.1mL vial – first 76mg/1.9mL vial 	Group A, Group A+B, Group C
	Follow-up period 
 Index date 	Study population

090177e1a4a71ff1\Approved\Approved On: 05-Nov-2025 14:15 (GMT)

Study Objective	Assessment period	Patient Exposure Groups
	
 • Index date (day 1) to day 8 • Day 9 to day 168 • Day 169 to end of follow-up period • Overall (day 1 to end of follow-up period) 	
Objective 3 – HCRU and costs	HCRU baseline assessment period	Study population
	SUD period 
 • Overall (Between first 44mg/1.1mL vial – first 76mg/1.9mL vial) • Between first 44mg/1.1mL vial – second 44mg/1.1mL vial • Between second 44mg/1.1mL vial – first 76mg/1.9mL vial 	Group A, Group A+B, Group C
	Follow-up period 
 • Index date • Index date (day 1) to day 8 • Day 9 to day 168 • Day 169 to end of follow-up period • Overall (day 1 to end of follow-up period) 	Study population
Objective 4 – Other MM treatments including supportive therapy	Follow-up period 
 • Index date • Index date (day 1) to day 8 • Day 9 to day 168 • Day 169 to end of follow-up period • Overall (day 1 to end of follow-up period) 	Study population
Objective 5 – Known adverse events	CRS/ICANS follow-up assessment period (CRS/ICANS events)	Group A, Group A+B, Group C
	SUD period (Cytopenia events) 
 • Overall (Between first 44mg/1.1mL vial – first 76mg/1.9mL vial) 	Group A, Group A+B, Group C

090177e1a4a71ff1Approved\Approved On: 05-Nov-2025 14:15 (GMT)

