Duration of treatment, patient level	Outcome	MDV	Days between first and last treatment administration for elranatamab (continuous)	Follow-up period
Duration of treatment, claim level	Outcome	MDV	Total calendar duration of elranatamb observation in days, and the date of the first observed elrantatamab claim	Follow-up period
Only 44mg/1.1mL vials [Summary statistic]	Outcome	MDV	Number of patients with only 44mg/1.1mL vials during the time period (yes/no)	Follow-up period
Only 76mg/1.9mL vials [Summary statistic]	Outcome	MDV	Number of patients with only 76mg/1.9mL vials during the time period (yes/no)	Follow-up period
Relative Administration Intensity (RAI) [Summary statistic]	Outcome	MDV	Ratio of the elranatamab administrations received divided by the expected number of administrations according to the Japan elranatamab label See Section 9.7.4 for more details	Follow-up period

Abbreviations: mL: millilitre; mg: milligram; RAI: Relative Administration Intensity; SUD: step-up dosing.

Table 5. Variables for Outcomes (Objective 3 – HCRU and Costs)

090177e1a4a71ff1\Approved\Approved On: 05-Nov-2025 14:15 (GMT)

Variable	Role	Data Source	Operational Definition	
			Definition	Assessment Period(s)
IP claim [Summary statistic]	Outcome	MDV	Number of patients with ≥ 1 all-cause IP claim (yes/no)	HCRU baseline period SUD period Follow-up period (overall only)
			Number of all-cause IP claims PPPM. Reported for all patients and for patients with ≥ 1 all-cause IP claim.	HCRU baseline period Follow-up period (overall only)
			Number of all-cause IP claims PPPD. Reported for all patients and for patients with ≥ 1 all-cause IP claim.	SUD period
OP claim [Summary statistic]	Outcome	MDV	Number of patients with ≥ 1 all-cause OP claim (yes/no)	HCRU baseline period SUD period Follow-up period (overall only)
			Number of all-cause OP claims PPPM. Reported for all patients and for patients with ≥ 1 all-cause OP claim.	HCRU baseline period Follow-up period (overall only)
			Number of all-cause OP claims PPPD. Reported for all patients and for patients with ≥ 1 all-cause OP claim.	SUD period

090177e1a4a71ff1\Approved\Approved On: 05-Nov-2025 14:15 (GMT)

Variable	Role	Data Source	Operational Definition	
			Definition	Assessment Period(s)
ED claim [Summary statistic]	Outcome	MDV	Number of patients with ≥ 1 all-cause ED claim (yes/no)	HCRU baseline period SUD period Follow-up period (overall only)

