9.7.3. Relative Administration Intensity

RAI will be calculated as the cumulative frequency of administration received over the expected number of administrations. Since response is needed to determine if switching to bi-weekly doses is appropriate and is not available in MDV, two schedule definitions will be used to estimate the expected number of administration to calculate RAI (Table 10. Dosing Schedule of Elranatamab during Follow-up Period for Patients Switching to

Q2W and Table 11. Dosing Schedule of Elranatamab during Follow-up Period for Patients staying on

QW Table 10. Dosing Schedule of Elranatamab during Follow-up Period for Patients Switching to

Q2W).

$$\text{RAI} = \frac{\text{Number of administrations received}}{\text{Number of expected administrations during the time period}}$$

a) Schedule 1¹

Assumption that all patients switch to bi-weekly doses (Q2W) after day 169 post-index.

Table 10. Dosing Schedule of Elranatamab during Follow-up Period for Patients Switching to Q2W

Follow-up Sub-Periods	Expected Administrations	Vial Size
Index date - Day 8	3 administrations	2 x 44mg/1.1mL 1 x 76mg/1.9mL
Day 9 - Day 168	1 administration per week	76mg/1.9mL
Day 169 – End of follow-up	1 administration every two weeks	76mg/1.9mL

Notes:

090177e1a4a71ff1\Approved\Approved On: 05-Nov-2025 14:15 (GMT)

¹ Adapted from dosing and administration guidance of the Japanese elranatamab label available at <https://labeling.pfizer.com/ShowLabeling.aspx?id=20462>

b) Schedule 2¹

Assumption that all patients continue with weekly doses (QW) after day 169 post-index.

Table 11. Dosing Schedule of Elranatamab during Follow-up Period for Patients staying on QW

Follow-up Sub-Periods	Expected Administrations	Vial Size
Index date - Day 8	3 administrations	2 x 44mg/1.1mL 1 x 76mg/1.9mL
Day 9 – End of follow-up	1 administration per week	76mg/1.9mL

Notes:

¹ Adapted from dosing and administration guidance of the Japanese elranatamab label available at <https://labeling.pfizer.com/ShowLabeling.aspx?id=20462>

Treatment exposure will be assessed across the different follow-up periods. End of follow-up is defined as the end of the hospital claim of the last elranatamab administration inclusive.

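### The RAI denominator can keep growing after the last dose when the final hospital claim is a multi-day stay, which biases RAI downward for those patients

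*Protocol*

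**What the plan says.** Section 9.7.3 defines the measure: "RAI will be calculated as the cumulative frequency of administration received over the expected number of administrations". Tables 10 and 11 supply the expected count. Both give "3 administrations" for index to day 8, then "1 administration per week". Schedule 1 changes to "1 administration every two weeks" from day 169. The last row of each table runs to the end of follow-up, and the section closes with: "End of follow-up is defined as the end of the hospital claim of the last elranatamab administration inclusive". Section 9.2 uses the same end point for the general follow-up period ("the end of the hospital claim of the last elranatamab administration").

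Two other places bear on this:

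- The text introducing Table 2 in Section 9.3.1 admits a patient to a follow-up sub-period on an elranatamab claim there "or if the end date of their follow-up period falls within" it.
- Table 4 stops patient-level duration of treatment at the last administration, not at the end of the claim.

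**The concern.** After the last administration the numerator of RAI is fixed. The denominator is not, because expected doses accrue until the claim closes. If that claim is an admission lasting beyond the last dose, the patient is charged with further expected doses. An outpatient who received the same doses on the same days, and whose claim closes on the dosing day, is not. RAI then depends partly on the discharge date.

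The error runs in one direction, downward. It is largest for patients who stop early while in hospital, because their denominator is small. RAI belongs to a primary objective and will be repeated in the low-weight subgroup (Section 9.7.5). Section 9.7.6 plans no sensitivity analysis that would expose the artefact. A low value would naturally be read as missed or delayed dosing.

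**Working it through.** The protocol states no RAI value, so there is no figure to reproduce. The check asks what the stated rule returns for a patient who missed nothing.

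**Which meaning of claim applies.** Section 9.2 defines each vial through a hospital claim, and Table 4 measures dosing intervals as days between claims; there a claim is a single dose record. Table 5, however, measures inpatient claims in days of stay. The second limb of the sub-period rule in Section 9.3.1 would add nobody if follow-up always ended on the day of the last dose, since that patient would already have a claim in the sub-period. The multi-day reading is therefore the better one, though not certain.

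**Inputs.** Three expected doses by day 8 and one per week thereafter (Tables 10 and 11). Last dose on day *L*; claim ending *t* days later. The protocol does not give *t*, so 0 to 28 days is assumed.

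**Formulas.** Received = 3 + (*L* − 8)/7. Expected = 3 + (*L* + *t* − 8)/7. RAI = received / expected. When *t* is a multiple of 7, counting completed weeks and counting pro rata give the same result.

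| Last dose | Received | t = 0 | t = 7 | t = 14 | t = 21 | t = 28 |
|---|---|---|---|---|---|---|
| Day 8 | 3 | 1.00 | 3/4 = 0.75 | 3/5 = 0.60 | 3/6 = 0.50 | 3/7 = 0.43 |
| Day 29 | 6 | 1.00 | 6/7 = 0.86 | 6/8 = 0.75 | 6/9 = 0.67 | 6/10 = 0.60 |
| Day 57 | 10 | 1.00 | 10/11 = 0.91 | 10/12 = 0.83 | 10/13 = 0.77 | 10/14 = 0.71 |
| Day 162, Schedule 2 | 25 | 1.00 | 25/26 = 0.96 | 25/27 = 0.93 | 25/28 = 0.89 | 25/29 = 0.86 |

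The first three rows hold under both schedules, because every window ends before day 169.

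**Dependence on the counting rule.** Last dose day 8, claim ending day 11 (*t* = 3): completed weeks give 3/3 = 1.00, pro rata gives 3/(3 + 3/7) = 0.875, and counting each started week gives 3/4 = 0.75. The protocol does not say which applies.

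**Sub-period day 9–168.** Last dose day 8, claim ending day 22: the patient enters only because follow-up ends there, with 0 received and (22 − 8)/7 = 2 expected, so RAI = 0.

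**Cohort mean, assumptions only.** Let a share *q* have a 14-day tail and everyone else score 1.00, so the mean is 1 − *q* + *q* × RAI.

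- Last dose day 8: *q* = 10% gives 0.90 + 0.10 × 0.60 = 0.96; *q* = 50% gives 0.50 + 0.50 × 0.60 = 0.80.
- Last dose day 57: *q* = 10% gives 0.90 + 0.10 × 0.833 = 0.98; *q* = 50% gives 0.50 + 0.50 × 0.833 = 0.92.

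**After closing the window at the last dose.** Here *t* = 0, and RAI is 1.00 in every row. Pro rata counting would still misbehave in short sub-periods: with a last dose on day 10, the day 9–168 value is 1/(2/7) = 3.5. Counting each started week as one dose gives 1/1 = 1.00.

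**The case against.** The best defence is that the claim may be the dose record itself. Section 9.2 and Table 4 use it that way, and Section 9.6 calls the database service-level. On that reading the gap is zero. This stands as a real ambiguity, but it leaves the phrase about the end of the claim, and the second limb of the sub-period rule, with no work to do.

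A second defence is that a patient still in hospital when the next dose falls due, and not dosed, has an observed undelivered dose that RAI may fairly count. Closing at the last dose is also a convention, and it can never register a final withheld dose. That is fair. But patients who stop as outpatients are never charged for undelivered final doses, so the present rule treats the two settings differently.

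Several stronger readings are tempting and are not supported:

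- That every patient whose last dose was inpatient is affected. The stay must run far enough to add an expected dose. If completed intervals are counted, a tail of 1 to 6 days on the weekly schedule costs nothing.
- That the extra days always fall after treatment ended. The protocol has no discontinuation date, and some patients will still be on treatment at the data cut.
- That Table 4 contradicts Section 9.7.3. Duration of treatment and RAI are different variables, and nothing requires them to share an end date. Table 4 shows only that the last administration date is already derived.
- That a published table will show low RAI for inpatients. Table 2 reports follow-up outcomes under Objective 2 for the whole study population, not by care setting, and no between-group comparisons are planned.

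**Conclusion.** The point holds in limited form. On the better reading of claim, the stated rule gives different RAI for identical dosing according to when the final claim closes, and the distortion is always downward. For one patient with no missed dose it can be large after early stopping (0.60 with 14 extra days after day 8) and is smaller after longer treatment (0.77 with 21 extra days after day 57).

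The size in this cohort cannot be computed. The assumed range of 10% to 50% of patients with a 14-day tail moves a mean of 1.00 to between 0.98 and 0.80, depending on when the last dose falls. Means are reported to one decimal place (Section 9.7.1), so 0.98 and 0.96 would both print as 1.0. A reader might infer that the RAI results will be seriously wrong overall; the protocol does not support that. It does support correcting the rule now, because the protocol itself fixes the end date for a variable under a primary objective.

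**What to change.** In Section 9.7.3, for RAI only:

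1. Close the window at the date of the last elranatamab administration.
2. Include a patient in a sub-period RAI only if the last administration falls in or after that sub-period.
3. Count expected administrations as whole doses, each dosing interval started up to the last administration counting as one.

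The end-of-claim definition stays for HCRU, where capturing the whole stay is sensible, and for the other objectives.

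The cost is a short text change and a small programming change, since administration dates are already needed for Table 4. Section 9.7 reserves protocol amendments for major changes to primary endpoint definitions or analyses; the sponsor should decide whether this is one.

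There are four limits:

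- Doses withheld during a final admission no longer lower RAI, as is already so for patients who stop as outpatients.
- Counting started intervals makes a one-day delay cost a whole dose when it ends the series: three doses by day 8 and a last dose on day 16 give 4/(3 + 2) = 0.80.
- Days 9 to 168 are 160 days, and 160/7 is not a whole number, so the weekly interval covering days 163 to 169 must be assigned to one sub-period only.
- The fixed expectation of three doses for days 1–8 is untouched, so a patient who stops after one or two doses still scores 1/3 or 2/3.

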9.7.4. Healthcare Resource Utilization and Costs

All-cause HCRU will be measured as the total number IP, OP, and ED that occurred over the follow-up period. Health claims will only be counted once per day to estimate visits. Additionally, the total length of IP stays will be reported among patients with at least one IP visit. Costs will be adjusted for inflation. More details will be provided in the SAP.

PPPM

PPPM standardizes HCRU and cost by calculating the average of a specific variable or a number of specific events (e.g., ED health claims, IP health claims) per month for each patient. In this study, PPPM will be used to report ED, IP and OP visits and cost for the HCRU baseline period and the follow-up period. To obtain PPPM, the following formula will be used for each patient:

$$PPPM = \frac{\text{Total number of events during a specified period}}{\text{Duration of the specified period (in months)}}$$

PPPD

PPPD standardizes HCRU and cost by calculating the average of a specific variable or a number of specific events (e.g., ED health claims, IP health claims) per day for each patient. In this study, PPPD

090177e1a4a71ff1\Approved\Approved On: 05-Nov-2025 14:15 (GMT)

will be used to report ED, IP and OP visits and cost for the SUD period. To obtain PPPD, the following formula will be used for each patient:

$$PPPD = \frac{\text{Total number of events during a specified period}}{\text{Duration of the specified period (in days)}}$$

This calculation will allow meaningful comparisons across patients with varying assessment period lengths, by normalizing resources use to a monthly rate. Summary statistics (mean, median, min, max) will then be reported to understand average monthly cost and utilization patterns across patients.

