9. RESEARCH METHODS

9.1. Study Design

This retrospective cohort study will assess the demographics, clinical history, SUD process, HCRU, and safety of elranatamab in MM patients with an elranatamab hospital claim. De-identified data from the Japan Medical Data Vision (MDV) will be used.

[figure not shown]
A retrospective cohort design was chosen because it allows for efficient use of existing RW data to evaluate treatment patterns and outcomes in a newly approved therapy, without the need for prospective data collection. This design is well-suited for descriptive analyses and enables timely insights into the early use of elranatamab in a RW setting.

The primary endpoints include patient demographics, clinical characteristics, and treatment patterns. Secondary endpoints include HCRU and safety outcomes. No formal measures of effect will be calculated. All analysis will be descriptive, with no a priori hypotheses or statistical comparisons between exposure groups.

The study population will be comprised of individuals aged 18 and older who initiated elranatamab between March 26, 2024, the PMDA approval date for elranatamab, and the end of data availability. The study period will be from the start of data availability, April 2008, to the end of data availability in MDV. The study period will remain the same for all study objectives. The patient baseline period will be from MM diagnosis to the start of the index treatment. The patient index date will be determined as the date of first hospital claim with an administration of elranatamab. The follow-up period will be defined as the period between the index date and the end of the hospital claim of the last elranatamab administration

inclusive. The SUD period will be defined as the period between the date of the first 44mg/1.1mL vial and the first 76mg/1.9mL vial of elranatamab, see more details in Section 9.2 and 9.3.1. Figure 1

Figure 1. Study design

Abbreviations: CCI: Charlson Comorbidity Index; HCRU: Health Care Resource Utilization; MM: multiple myeloma; SUD: Step-up dosing;

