9.2.1. Inclusion Criteria

Patients must meet all of the following inclusion criteria to be eligible for inclusion in the study:

1. First hospital health claim with an administration of elranatamab on or after March 26, 2024.
2. Have a diagnosis of MM.
3. Aged ≥ 18 years at the time of first hospital claim for elranatamab (i.e., index date).

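### The unweighted mean PPPM over follow-up can be materially inflated by a few patients with very short follow-up; add the pooled rate beside the median

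*Protocol*

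**What the plan says.** Section 9.7.4 sets the calculation at patient level: "To obtain PPPM, the following formula will be used for each patient". The numerator is that patient's event total and the denominator is "Duration of the specified period (in months)". On scope, "PPPM will be used to report ED, IP and OP visits and cost for the HCRU baseline period and the follow-up period"; Table 5 limits the follow-up visit-count and cost summaries to the overall period. The patient values are then summarised: "Summary statistics (mean, median, min, max) will then be reported to understand average monthly cost and utilization patterns across patients". Section 9.7.1 adds the SD and IQR for continuous variables. Section 9.7.4 presents the calculation as a way to compare patients whose periods differ in length.

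Section 9.2 ends follow-up at "the end of the hospital claim of the last elranatamab administration", and section 9.1 counts that end inclusively. On the start, section 9.1 says: "The patient index date will be determined as the date of first hospital claim with an administration of elranatamab". The entry condition in section 9.2.1 is "First hospital health claim with an administration of elranatamab on or after March 26, 2024", with no minimum number of doses or days. Table 1 keeps patients who received only 44 mg vials in the study population, which Table 2 uses for follow-up HCRU. Section 9.2 shortens the 180-day HCRU baseline window to whatever data are available. Section 9.7.6 plans no sensitivity analysis.

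**The concern.** A mean of individual ratios gives each patient the same weight, however little time stands behind the ratio. Here the start of follow-up is itself a claim, so every patient has at least one event in the numerator of the all-claims count. The denominator can be as small as one day. A patient seen once and never again then gets the same visit rate as a patient seen every day for six months.

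What is at stake is Objective 3. A reader will naturally take the mean PPPM visits and mean PPPM cost over follow-up as the average per month of treatment. If a few patients stop after one administration, or start just before the data cut, the mean can sit well above the total visits or cost divided by the total months observed. Nothing in the planned output would show the gap.

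**Working it through.** The protocol gives no PPPM figure, so there is nothing to reproduce. The check compares the planned mean with the pooled rate.

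**Inputs from the protocol.** PPPM for patient i is events_i / months_i, summarised without weights (9.7.4). There is no minimum duration (9.2, 9.2.1). The last day is counted inclusively (9.1). Visits are counted at most once per day (9.7.4). The February 2025 data cut held 128 patients with an elranatamab claim (9.5).

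**Assumptions not in the protocol.** One month is 30.4375 days. An outpatient claim begins and ends on the day of the visit. Most patients have 180 days of follow-up with one visit per week. A share p has 1 day of follow-up with one visit. The values of p are 2%, 5% and 10%, or about 3, 6 and 13 of 128.

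**One visit, by length of follow-up.** PPPM = 30.4375 / days. This is 30.4 at 1 day, 15.2 at 2 days, 4.35 at 7 days, 2.17 at 14 days and 0.17 at 180 days.

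**Weekly visits.** The long-follow-up rate is 30.4375 / 7 = 4.35.

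- Planned mean = (1 − p) × 4.348 + p × 30.4375
- Pooled rate = [(1 − p) × 180/7 + p] / [(1 − p) × 180 + p] × 30.4375

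| p | Planned mean | Excess over 4.35 | Pooled rate |
|---|---|---|---|
| 2% | 4.261 + 0.609 = 4.87 | +12% | 25.220 / 176.42 × 30.4375 = 4.35 |
| 5% | 4.131 + 1.522 = 5.65 | +30% | 24.479 / 171.05 × 30.4375 = 4.36 |
| 10% | 3.913 + 3.044 = 6.96 | +60% | 23.243 / 162.10 × 30.4375 = 4.36 |

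At p = 5% the short patients hold 0.05 / 171.05 = 0.03% of the patient-time. The median stays at 4.35 in all three rows, because well under half of the patients are affected. If the short follow-up is 7 days with one visit, that patient's PPPM is 4.35 and the mean is not distorted.

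**Direction by outcome.** Take IP claims, assuming 1.5 per 180 days for long-follow-up patients: 1.5 / (180 / 30.4375) = 0.254 PPPM. Let 6 of 128 patients have short follow-up.

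- Short patients have 1 outpatient day and no admission: mean = 122 × 0.2536 / 128 = 0.242; pooled = 183 / (21,966 / 30.4375) = 0.254. The mean is slightly lower.
- Short patients have one 7-day admission: mean = (122 × 0.2536 + 6 × 4.348) / 128 = 0.446; pooled = 189 / (22,002 / 30.4375) = 0.261. The mean is 1.7 times the pooled rate.

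**Cost.** If the only day costs c, PPPM cost for a 1-day patient is c / (1 / 30.4375) = 30.4 c. The documents hold no cost figures, so the effect on mean cost cannot be sized further.

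**PPPD.** Section 9.7.4 uses PPPD for the SUD period, and Table 2 limits that analysis to Groups A to C, which require both vial sizes. In Group A two gaps of 1 to 7 days give 1 + 1 + 1 = 3 to 7 + 7 + 1 = 15 days inclusive. The unit is a day, so there is no scaling up to a month.

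**The case against.** Four points on the other side have force.

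First, a reader might infer that the mean is the plan's headline figure for monthly cost. The text does not say so: mean, median, minimum and maximum are listed together with no order of importance, and the median resists a few extreme values. This stands, and it limits the point to interpretation of the mean.

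Second, a reader might infer that short-follow-up patients dominate the mean for every outcome. The documents do not support that. They give no distribution of follow-up length. An inpatient dose extends follow-up to the end of that claim, so 1-day denominators arise mainly with outpatient dosing or very short stays. An outpatient-only patient lowers mean IP PPPM instead of raising it. This also stands, so the figures above are illustrations.

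Third, the mean of patient rates is a legitimate quantity with equal weight per patient, and the pooled rate is a different, time-weighted one. So the plan contains no arithmetic error. But section 9.7.4 offers the measure for comparing patients with unequal periods and for describing average monthly cost and use. The unweighted mean serves that aim poorly when some periods last a day. A claim that the mean will drift between interim and final analyses would not separate the two measures, because a pooled rate also moves if use is concentrated early.

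Fourth, section 9.7.4 leaves further detail to the SAP, which is not shown and might set a minimum duration. That is possible, but the per-patient formula and the list of summaries are already fixed in the protocol.

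**Conclusion.** The point holds as a limited one. As written, the unweighted mean PPPM for follow-up can be materially inflated by a few patients with very short follow-up: about +12% to +60% for visits if 2% to 10% of patients have a 1-day follow-up and the rest are seen weekly over 180 days. Those shares and visit patterns are assumptions. The mechanism follows from the protocol's own definitions; the size does not. It varies by outcome, can reverse for IP claims, and vanishes when short follow-up has the same visit rate as long follow-up. The planned median is largely unaffected. Baseline PPPM is open to the same effect where the 180-day window is cut short. Objective 3 is secondary and descriptive, so this is a cheap improvement and no threat to the study.

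**What to change.** In section 9.7.4, for follow-up and HCRU baseline PPPM, add the pooled rate as the estimate of average monthly use and cost: total events (or total cost) divided by total patient-months. A bootstrap interval is optional in a descriptive study. Keep the per-patient median and IQR to describe spread, and state that the unweighted mean is not to be interpreted alone. Leave PPPD as it is.

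The cost is one formula and one more line per table, with no new data. The drawback is that the pooled rate weights patients by follow-up time, so patients who stop early count for little. The report should say so.
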